A meta-analysis of studies using music for the treatment of neurological language and speech disorders showed that although measurable improvement was reported, the methodological quality of studies was rated low (Hurkmans et al., 2011). Specific recommendations were made to report education, dominance, and musical background, all of which were included in the current study. Education was reported based on highest level of formal education attained. Dominance was determined by premorbid handedness for writing. Musical background included reporting previous formal instruction for singing/choir, playing an instrument, or reading music, and experience with performance of singing, dancing, and listening to music.

Sample Size

A minimum of four participants was required to demonstrate replication of treatment effects (Gast & Ledford, 2014, p.327). A maximum of ten participants was requested from the Internal Review Board (IRB) to account for attrition. This study reports on the first two participants of the approved trials.

Environment

The physical environment was the Out-Patient Rehabilitation clinic in the ST office which is also a private treatment room (for Participant #2), and the patient's home when served by home health (for Participant #1). The clinic was located at the end of a hallway away from the other therapies so there was little noise or commotion. The SLP and client both sat at a large table with a minimum of materials laid out. The room was well-lit with no windows. Limited use of bright color added appeal without drawing undue attention. Distractions were kept to a minimum, but included training materials and a desk-top computer behind the therapist. All other materials were kept in a closed cabinet and filing cabinet. The patients and significant others were seated in various locations at the table to best accommodate vision and hearing. Home settings were controlled for lighting, sound, and undue distractions to the maximum extent possible.

Independent Variable:

The independent variable was manipulated to contrast three conditions:

1. Polyphonic music with song lyrics presented simultaneously with silent reading and observation of pointing to written lyrics (independent processing condition);
2. Priming with polyphonic music with lyrics followed by silent reading and observation of pointing to written lyrics (shared processing condition);

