3. A limited control set using listening to oral reading of the lyrics and silent reading of the written lyrics with observation of pointing to written lyrics (no music).

Dependent Variables:

The dependent variable was defined as silent reading/comprehension of targeted words/phrases by pointing to words/phrases in a phrase completion exercise without music. The dependent variable was kept constant for all three conditions.

Dependent Measures

Measurement of the dependent variable consisted of both direct systematic observational recording (DSOR) and treatment record video (for reliability/procedural fidelity assessment) of percentage correct over time (including follow-up) and trials- or sessions-to-criterion.

Research Design

An AATD was used for comparison of two separate but similar conditions when the effects may be non-reversible (see Gast & Ledford, 2014, pp. 324-332). Time between sessions was at least a day.

“Criteria:

1. Behaviors must be non-reversible—the behaviors will continue to be performed after instruction has stopped.
2. Behaviors should not be in the participants' repertoire.
3. Behaviors must be independent, meaning one behavior set/chain can be acquired without influencing performance on other behavior sets/chains.
4. Behaviors also must be functionally equivalent, meaning behaviors are likely to be influenced by the same environmental variable (e.g., the instructional strategies being studied).
5. *Behavior sets/chains must be of equal difficulty.* The dependent variable in this investigation will be phrases acquired, but three different sets will be required to fulfill the requirement that the behaviors are independent. To ensure that they are of equal difficulty, they must all be assessed for word complexity at a minimum.

Randomizing items between treatment conditions should result in a relatively equal distribution of difficulty” (Romer, Billingsley, & White (1988).

Procedures

All songs were pretested for familiarity and positive valence by questioning the participants (i.e. Do you know this song? Do you like it?). Response data was recorded. All songs perceived as not liked were eliminated and substitutions made; the new songs were then also pretested for familiarity and positive valence. Songs that were not familiar but were liked were noted but not changed.

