During the intervention (B), each song (music with lyrics) from set 1 (B1) was played in its entirety. When the targeted verse or chorus played, the written lyrics were simultaneously shown along with the song lyrics. The SLP pointed to the words of the targeted verse/chorus which was silently observed by the participant as they were sung. This was repeated for all ten songs. The phrase completion task was then presented, including the total 25 phrases, without music. The participant silently or orally read the phrase and circled the phrase completion choice. Correct responses were randomly verbally reinforced. Error responses were followed by verbal modeling and pointing to the correct choice by the SLP. The next session, each song (music with lyrics) from set 2 (B2) was played in its entirety. After the song played, the written lyrics from the targeted verse or chorus were presented. The SLP pointed to the words of the targeted verse/chorus which was silently observed by the participant. This was repeated for all ten songs. The phrase completion task was then presented, including the total 25 phrases. The participant silently or orally read the phrase and circled the phrase completion choice. Correct responses were randomly verbally reinforced. Error responses were followed by verbal modeling and pointing to the correct choice by the SLP. This was repeated for all ten songs. For all interventions, the number of correct responses were tallied on a LaPoint Base 10 form and the percent correct entered on the graph for that day. The same procedures were repeated, alternating procedures on sets 1 and 2 on subsequent treatment visits, until a criterion of 9/10 (90%) x 3 consecutive visits was reached on both sets. It was predetermined that if the criterion was not reached on one of the intervention sets, defined as no increase in percentage correct x 3 consecutive visits, that intervention would be considered to be limited in effectiveness and discontinued. Every third session was digitally recorded for a reliability check by the trained assistant. When both of the sets (B1 and B2) had been acquired or one acquired and the other discontinued, the number of sessions to criterion were counted for each intervention.

Potential Threats to Internal Validity

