Potential threats to internal validity included multiple-treatment interference in the form of sequential confounding and carryover effects. Counterbalancing conditions was necessary, and any carryover effects identified (see Gast & Ledford, 2014, chapter 5 p.101). Because AATD studies test efficiency, the goal involves demonstrating optimal performance as opposed to artificially deflated performance, so responses were reinforced during the baseline phase (see Gast & Ledford, 2014, p. 326).

Potential threats to internal validity also included possible history or maturation effects. A control set was used to rule out history and maturation effects.

Outcome Measures and Time Points

Pretest/post-test information on the ICF Body Functions/Structures, Activities, and Participation was provided (Hurkmans et al. 2011). The Boston Diagnostic Aphasia Examination (BDAE) (Goodglass, Harold, & Kaplan, 1983) was used as an outcome measure of reading acquisition. The BDAE is a classic anatomically-based diagnostic instrument. Because various components of language function may be selectively damaged by CNS lesions, results indicate the neuro-anatomical organization of language and localization of the lesion. Thus it serves as an appropriate assessment for research exploring neurological organization in the brain. Pretest reading scores on selected subtests from the BDAE full version were completed prior to baseline A and initiating intervention, and immediately following completion of intervention to assess generalization to non-trained stimuli. At four weeks follow-up the trained stimuli from all three interventions was retested to assess retention. The dependent variables, that is differential response to the two interventions (counted as the percent correct responses per day, a ratio scale which has equal intervals and an absolute zero, which allows for multiplication and division so is appropriate for averages), number of sessions required to achieve mastery at each level (simple counting but also a ratio scale as it has equal intervals and an absolute zero which allows for multiplication and division so allows for the difference between means), retention of the material (number of items remembered, another simple count which is also a ratio scale as it has equal intervals and an absolute zero and allows for the difference between means), was assessed using data analysis as described below.

Data Analysis

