- The difference in number of sessions/trials to achieve mastery at each level for each intervention, and the difference in retention at three weeks follow-up were analyzed by comparison of the difference between data points for the control treatment and the two target intervention conditions. After the research design has been completed by a minimum of four subjects, data will be consolidated for group means.

Data Storage

Patient telephone numbers were accessible in the participants' soft file for patient contact while the patient was undergoing speech therapy treatment, as is common practice. On discharge the soft file was stored in the hospital Medical Records Department.

Participants' performance on the phrase completion task was videotaped every third visit using the hospital emergency iPad. The iPad was checked out in the morning before the participant's treatment session. The last treatment trial (for procedural fidelity) and the participant's responses to the phrase completion task (for inter-observer reliability) were recorded and stored in the speech therapy office in the Rehab building until viewed by the assistant in a private location and recorded on the paper reliability data forms. The digital recording was then deleted and the iPad returned. Digital videos did not show participant faces, only hands on the response task were recorded.

Role of the researcher

The primary investigator (PI) pre-selected candidates for participation according to the stated recruitment procedures (above). The rehabilitation manager recruited participants, but the PI obtained informed consent. Given the therapy location, the PI conducted the experimental treatments, making adjustments to the protocol based on preliminary findings as necessary, with IRB approval for any changes. The PI was also responsible for training the (blinded) assistant for reliability checks from videotapes, and interpreting and reporting the data.

Assumptions and Limitations

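### The control set is defined as a trained no-music reading condition, but the procedure describes no training for it, so what the music-versus-control comparison measures is unsettled

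*Combined protocol and SAP*

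**What the plan says.** The Independent Variable section states: "The independent variable was manipulated to contrast three conditions". Two are music conditions, simultaneous and priming. The third is "A limited control set using listening to oral reading of the lyrics and silent reading of the written lyrics with observation of pointing", labelled as having no music. Two later sections use language that fits a trained third set. Outcome Measures and Time Points says that at follow-up "the trained stimuli from all three interventions was retested to assess retention". Data Analysis plans, for sessions to mastery and for retention, a "comparison of the difference between data points for the control treatment and the two target intervention conditions".

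Other parts describe something different. Research Design says "An AATD was used for comparison of two separate but similar conditions". The intervention part of Procedures sets out a session for set 1 and a session for set 2, then says "The same procedures were repeated, alternating procedures on sets 1 and 2 on subsequent treatment visits". It applies the criterion of 9/10 on three consecutive visits to those two sets and counts sessions to criterion for B1 and B2. It gives no control session, exposure or criterion. The control phrases do appear in the 25-phrase test that follows each music session, and the correction of errors by modelling and pointing does not exempt them.

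Potential Threats to Internal Validity gives the set a further job: "A control set was used to rule out history and maturation effects". Assumptions and Limitations repeats this and names spontaneous recovery as an example of maturation.

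**The concern.** The definition of the condition and the procedure for delivering it do not agree, and the meaning of the planned comparison depends on which was followed. The music sets receive written lyrics, guided pointing and the therapist's attention as well as music. A control that receives the same without music isolates the music. A control that is only tested, with errors corrected, does not.

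The title asks about the effect of music on reading comprehension. If the procedure was run as written, a favourable difference would be open to being read as a music effect even if reading the lyrics aloud with pointing would have done as well. One of the two endpoints in the control comparison, sessions to mastery, would also have no control value to enter.

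**Working it through.** The documents give no power or effect-size figure on this point, so there is nothing to reproduce. The check sets the sections side by side and then asks what the planned difference estimates under each reading.

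**1. Is the control set trained?**

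| Section | Implication |
|---|---|
| Independent Variable | Trained: oral reading heard, silent reading, pointing observed |
| Research Design | Two conditions compared |
| Procedures, intervention phase | Sessions, alternation, criterion and session count for sets 1 and 2 only |
| Potential Threats; Assumptions and Limitations | Set rules out history and maturation |
| Outcome Measures and Time Points | Trained: one of three interventions |
| Data Analysis | A control treatment, compared on mastery and retention |

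No section reconciles these.

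**2. What does the difference estimate?** Assume additive gains: *h* common to all sets (maturation, history, repeated testing, error feedback), *t* from lyric training without music, and *m* from music.

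- Music set: *h + t + m*.
- Control trained as defined: *h + t*. Difference = (*h + t + m*) − (*h + t*) = *m*. The shared *h* cancels. The control's own gain, *h + t*, includes teaching and does not measure maturation by itself.
- Control without lyric training: *h*. Difference = (*h + t + m*) − *h* = *t + m*. The control's own gain is closer to a maturation measure, but still includes testing and feedback.

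With assumed values in percentage points:

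| *t* | *m* | Control trained | Control not trained |
|---|---|---|---|
| 10 | 0 | 0 | 10 |
| 20 | 0 | 0 | 20 |
| 30 | 0 | 0 | 30 |
| 10 | 10 | 10 | 20 |
| 20 | 10 | 10 | 30 |
| 30 | 10 | 10 | 40 |

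In the untrained case the excess over the music effect is always *t*.

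**3. Training visits described.** Alternation starting with set 1 gives ceil(V/2) visits to set 1 and floor(V/2) to set 2 out of V visits. For V = 6, 12 and 17 this is 3 and 3, 6 and 6, and 9 and 8. Described control-training visits are 0 in each case, while testing with feedback covers all sets at all V visits. These totals are illustrative. The figure of 17 comes from the definition of normal progress used for monitoring under Human Rights Protections. Training ends on criterion or discontinuation, and no total is fixed.

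**4. Is sessions to mastery defined for the control?** The procedure states no criterion for it, and the 9/10 rule does not carry over by itself. If each of the ten songs per music set supplies one phrase (an assumption, as the phrase appendix is not in the documents), the control has 25 − 10 − 10 = 5 phrases. It then moves in steps of 100/5 = 20 points and meets 90% only at 5/5. With 9 to 10 phrases in set 1 and 10 to 11 in set 2, the control has 4 to 6 phrases, and 90% still requires every item correct.

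**5. The two music conditions.** Their comparison uses sets 1 and 2, both of which have sessions, a criterion and a session count. The control does not enter it.

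**The case against.** The strongest reply is that the procedure is merely incomplete. The definition of the condition, the follow-up wording and the analysis wording all imply that the control was trained, against one omission. If so, the difference addresses music. This stands to the extent that silence in the procedure is not evidence of zero delivery. A reader might infer that the control set received no training, or that the music sets had 9 and 8 sessions against none. The documents support only that no control session is described, and the visit counts are not a planned schedule.

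A reader might also infer that serving as a no-music comparator and ruling out maturation are wholly incompatible. They are not. A trained control still removes shared history and maturation from the between-set difference. What it cannot do is show through its own gain how much was maturation.

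Nor would it be right to call the set untouched or probe-only, since its errors are corrected at testing. That feedback does not supply the missing condition, which is defined as hearing the lyrics read aloud while following the text.

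Calling the control *limited* does not settle the matter either, because the same item goes on to list the training it receives.

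Finally, the design is mainly a comparison of two music conditions, and that comparison is unaffected. This limits the scope of the point. It does not remove it, because Data Analysis plans the control comparison.

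**Conclusion.** The point holds as an inconsistency that decides what the music-versus-control comparison means. Under the written procedure, the difference equals the music effect plus the whole effect of lyric training without music, so it cannot be attributed to music, and sessions to mastery is undefined for the control. If the defined reading condition was delivered, the difference does address music, and only the claim about maturation needs narrowing.

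The documents do not establish which of these happened. They therefore do not support a flat statement that music cannot be isolated, or a finding against the study as a whole. The size of the bias in the untrained case is *t*, shown above for an assumed 10 to 30 points. The argument assumes additive gains and a common *h* across sets. It does not depend on the number of visits. It should be settled before the control comparison is interpreted or pooled.

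**What to change.** First, state what was done: whether the control reading condition was delivered, on which visits, and with what exposure per phrase. Then bring Independent Variable, Research Design, Procedures, Potential Threats to Internal Validity, Outcome Measures and Time Points, Data Analysis, and Assumptions and Limitations into line with the answer.

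- **(a) Not delivered.** Describe the set as *no lyric training; tested with error feedback at every visit*. Change the three conditions, and the three interventions at follow-up, to two. Drop the control from the sessions-to-mastery comparison. Limit conclusions to simultaneous versus priming, and to music-plus-text training versus testing with feedback only, with no claim for music itself.
- **(b) Delivered, or to be delivered.** Write it into the intervention procedure, with exposure per phrase matched to the music sets and a mastery criterion suited to the size of the control set. Say that history and maturation are ruled out for the between-set difference, not measured by the control's own gain.

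Option (a) costs wording and a narrower conclusion. Option (b) costs wording if the condition was already given as needed, and otherwise some added session time, which cannot be sized because no visit total is fixed. The report covers the first two participants and group means wait for at least four, so the clarification can be made before any pooling.

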During the baseline (A) all 25 phrases (Appendix C) were tested using the phrase completion task (Appendix D). Both correct responses and participation were verbally reinforced, as is required in an AATD. Results were analyzed by the SLP to ensure that the sets were of equal difficulty for each participant using two different procedures. First, logical analysis of the linguistic characteristics of the phrases was completed, including the number of words, the number of syllables in the words, the number of consonant blends in the words, and the number of contractions. Second, experimental evaluation of the number of error responses in each set during the baseline phase was completed, and without changing the items or responses, the set assignment was manipulated to maximally equate the number of error phrases without significantly changing the equivalency of the linguistic characteristics. One phrase was shifted from set 1 to set 2 during the baseline phase. In the end, the number of error responses on baseline for set 1 was three, for set 2 was two, and for the control set was two.

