The role of the primary investigator presents the possibility of a threat to construct validity in the form of potential experimental bias, either by expectations of the subjects via the Hawthorne effect, or from unintentional experimenter effects. To reduce this threat, participants were blinded to the exact purpose of the experiment until all data was collected, and reliability checks of measurement data were conducted by an assistant blinded to the purpose of the study, but the study could still be limited by experimenter effects. Given a significant result of this investigation, follow-up systematic replication studies will be conducted in other locations with other skilled therapists performing the same experimental treatments.

Threats to internal validity included possible history or maturation effects. History effects are extraneous events prior to post-test that can affect the DV. Maturation effects are changes in the DV resulting from the passage of time, e.g. spontaneous recovery. In AATDs, a control set is used to rule out history and maturation effects.

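### Phrases were reallocated between the two music sets by the treating investigator after baseline errors were known, with no documented random or concealed step, so sessions to criterion is open to selection bias

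*Combined protocol and SAP*

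**What the plan says.** Under Research Design, the fifth criterion requires sets of equal difficulty: "To ensure that they are of equal difficulty, they must all be assessed for word complexity at a minimum". The same quoted block ends with a remark attributed to a cited source: "Randomizing items between treatment conditions should result in a relatively equal distribution of difficulty".

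Under Procedures, the baseline paragraph describes what was done: "Results were analyzed by the SLP to ensure that the sets were of equal difficulty for each participant using two different procedures". The first procedure was a comparison of linguistic counts. The second used the participant's own baseline errors: "the set assignment was manipulated to maximally equate the number of error phrases", provided that the linguistic match between sets was not materially disturbed. The outcome was that "One phrase was shifted from set 1 to set 2 during the baseline phase". Baseline errors then stood at three in set 1, two in set 2 and two in the control set.

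The intervention paragraph of Procedures ties set 1 to simultaneous music and set 2 to priming. It sets mastery at 9/10 on three consecutive visits and counts sessions to criterion for each intervention.

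On roles, Participant Recruitment (item 6) has the SLP conducting consent, while Role of the researcher has the PI obtaining it. Read together, these indicate one person. Role of the researcher adds that "the PI conducted the experimental treatments, making adjustments to the protocol based on preliminary findings as necessary" (subject to IRB approval) and that the PI interprets the data. Assumptions and Limitations describes participants as blinded to the exact purpose, and says "reliability checks of measurement data were conducted by an assistant blinded to the purpose of the study". It does not list the PI as blinded.

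**The concern.** In this design the phrase is what gets allocated to a condition. Here the allocation was adjusted by someone who knew which phrases the participant had missed, knew which condition each set would receive, and would go on to treat and interpret. That is allocation without concealment, at the level of the item.

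The balancing rule limits this only in part. It fixes how many missed phrases each set holds and keeps the sets linguistically similar overall. It does not fix which missed phrases sit where, and two sets with similar error counts can still differ in how learnable those phrases are. Phrases already correct at baseline contribute little to time to mastery, so sessions to criterion depends on a handful of items. A difference that arises from their placement would be read as a difference between music conditions. If the same person adjusts the sets in the same way for each participant, pooling over four or more participants would not remove a consistent tilt.

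**Working it through.** **Inputs from the documents.** 25 phrases; baseline errors 3/2/2 after the adjustment, 7 in total; one phrase moved from set 1 to set 2; criterion 9/10 (all from Procedures). The item-level baseline data are not shown, so 3/2/2 cannot be re-derived, and there is no power figure to reproduce.

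**Inferred.** Ten phrases in each music set (from 9/10 and the ten songs per set), hence 25 − 10 − 10 = 5 in the control set.

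**Step 1: distance to criterion.** Set 1 starts at (10 − 3)/10 = 70% and needs two of its three missed phrases. Set 2 starts at (10 − 2)/10 = 80% and needs one of its two. At most five phrases therefore decide the comparison.

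**Step 2: the position before the move.** The documents do not say whether the moved phrase was a baseline error.
- If it was, counts went from 4/1/2 to 3/2/2, and the investigator had four candidates.
- If it was answered correctly, the counts were 3/2/2 before and after, and no error phrase changed set.

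**Step 3: what the choice among four could do (illustration).** Assumptions: the seven missed phrases take 1, 2, …, 7 visits to learn, stay learned, and are learned equally fast under either condition. Then:
- T1 = second smallest learning time among the three errors left in set 1
- T2 = smallest learning time among the two errors in set 2
- D = T1 − T2, the difference in first visit at 9/10

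Example: set 1 starts with learning times 2, 3, 5, 6 and set 2 with 4.

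| Phrase moved | Set 1 left | T1 | Set 2 | T2 | D |
|---|---|---|---|---|---|
| 2 | 3, 5, 6 | 5 | 2, 4 | 2 | +3 |
| 3 | 2, 5, 6 | 5 | 3, 4 | 3 | +2 |
| 5 | 2, 3, 6 | 3 | 4, 5 | 4 | −1 |
| 6 | 2, 3, 5 | 3 | 4, 6 | 4 | −1 |

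All four choices end at 3/2/2, yet D swings by 3 − (−1) = 4 visits and changes sign.

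There are 7!/(4!·1!·2!) = 105 starting arrangements. Over all of them the swing between the largest and smallest D runs from 1 to 8 visits, with median 4 and mean 4. It exceeds 7 in only 3 of the 105.

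**Step 4: the actual criterion.** The protocol requires three consecutive visits at 9/10. If learned phrases stay learned, this adds two visits to both T1 and T2 and cancels in D. If performance fluctuates from visit to visit it need not cancel, so the figures remain illustrative.

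**Step 5: what random allocation would and would not change.** Under the same assumptions there are 7!/(3!·2!·2!) = 210 ways to reach 3/2/2. Over these, D runs from −4 to +5 with mean +1.33. A random draw that lands on 3/2/2 shares that spread, and the positive mean comes from three errors against two. Randomising removes the chance to steer, but not the chance spread within one participant.

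**The case against.** Several points on the other side stand.

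- **No broken commitment.** A reader might infer that the plan promised to randomise items and then did otherwise. The documents do not support that: the sentence is quoted background on the design. The requirement is equal difficulty, and the Procedures section does assess it. What can be said is that a recommended step is cited and no random step is described. How the initial sets were formed is not stated either, so a non-random step is shown only for the adjustment.
- **Matching on errors is legitimate.** It addresses equal difficulty directly. Simple randomisation of 25 phrases to sets of 10/10/5 with seven errors would leave a gap of three or more errors between the music sets with probability 0.22. If the moved phrase was an error, the move cut that gap from 4 − 1 = 3 to 3 − 2 = 1. This argues against unstratified randomisation, but not against a stratified draw.
- **The move was small and early.** One phrase is reported moved, during baseline, under a stated rule. That excludes tuning on intervention results. It does not exclude knowing which phrases were missed and which condition they would join.
- **Steering needs foresight.** To exploit the choice, the investigator would have to guess which missed phrases would be learned soonest. The documents describe no information on this beyond the linguistic counts, which the rule already constrains. The swings above are therefore what is possible, not what is likely.

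A reader might also take the whole −4 to +5 range over 210 splits as the size of the bias. It is not: the reported move offered at most four choices if one error phrase moved, and random allocation has the same spread.

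**Conclusion.** The point holds as a weakness in allocation and reporting. Set membership was adjusted by hand, using baseline responses, by a treating investigator not described as blinded, and no random or concealed step is documented for phrases or for pairing matched sets with conditions. Sessions to criterion is thereby open to selection bias. A reader might infer that the priming condition was favoured; the documents do not show this, and Assumptions and Limitations already concedes possible experimenter effects in general terms.

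The size cannot be estimated from the documents. The illustrative swing of 1 to 8 visits, median 4, rests on four things: that the moved phrase was a baseline error, ten phrases per music set, invented learning times of 1 to 7 visits, and no treatment effect. If the moved phrase was answered correctly at baseline, that mechanism did not operate for this move.

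The change is worth making because it is nearly free and can still help. Two participants are reported, four is the stated minimum and ten the approved maximum (Sample Size), leaving two to eight to come.

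**What to change.** **Remaining participants.** In the baseline paragraph of Procedures, replace the manual shift with computer-generated random allocation of phrases to set 1, set 2 and control. Stratify by baseline result (error or correct) and by the linguistic counts already made, grouped coarsely enough for 25 phrases. Where errors do not divide evenly, draw at random which set takes the extra one. Existing study staff who do not treat, such as the rehabilitation manager, should draw the list. Lock it before the first intervention visit, with no later moves.

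**Participants already run.** Report:
- how the initial sets were formed;
- which phrase moved and whether it was a baseline error;
- set sizes before and after the move;
- which participant the 3/2/2 counts describe, since Procedures speaks of each participant but gives one set of counts;
- sessions to criterion with the moved phrase excluded. If this leaves nine phrases in set 2, state how the 90% criterion is applied, because 8/9 = 88.9% falls short and 9/9 meets it.

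**Cost.** A short wording change and a few minutes per participant. The linguistic counts may match slightly less exactly than by hand. Chance differences between sets within one participant will remain and should be acknowledged when results are read.
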